Protocol

A) CLINICAL TRIAL IDENTIFICATION

Title	Use of Music Therapy as an Intervention to Reduce Anxiety in Patients With Localized Breast Cancer		
Short title	CENSORIAL		
Coordonnateur	[name] Study nurse ICO Site Angers [contact]		
Estimated number of centers	1	Number of subjects	27
Inclusion period	18 months	Overall duration	24 months
Subject participation duration	5 months		

B) SPONSOR IDENTIFICATION

Sponsor name	ICO, DRC-Cellule de Promotion
Contact	[name] [name] [contact]

C) SYNOPSIS

Breast cancer is the most common cancer among women worldwide, with 58,500 new cases reported in metropolitan France in 2018. The diagnosis of cancer, the explanation of treatment modalities, and their potential adverse effects can generate distressing emotions, such as fear, and the resources available to cope with these emotions vary among patients. Attending the hospital for outpatient chemotherapy administration is, in itself, a potential source of anxiety.

The use of music as part of a therapeutic approach constitutes an intervention that may help patients reduce the intensity of distressing emotions. "Active" music therapy involves the patient's participation through the use of instruments, vocal expression, or rhythmic body movement, without requiring any prior musical skills. The presence of a certified music therapy professional is essential, particularly to support and manage the emotions that may arise during sessions. These sessions may be conducted individually or in groups. In the context of breast cancer, music therapy has demonstrated benefits in reducing pain, anxiety, depressive symptoms, and length of hospital stay in patients undergoing mastectomy.

⇒ **This controlled, randomized study aims to assess the effect of music therapy on reducing anxiety in patients with localized breast cancer receiving outpatient chemotherapy, compared with a control group without musical intervention.**

D) INFORMATION

Design	The study has the following characteristics: 
 • Single-center study • Controlled study • Randomized study (2:1 allocation ratio) • Open-label study • Prospective study • Parallel-group design
Primary objective	To evaluate the effect of music therapy on anxiety levels in patients with breast cancer receiving adjuvant or neoadjuvant chemotherapy.

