Primary endpoint	Anxiety will be assessed using the STAI scale (Trait form YB and State form YA). The STAI State score will be collected before and after chemotherapy administration during the first three chemotherapy sessions in both the music therapy and control

	groups. The mean pre- and post-chemotherapy difference in STAI State scores will be compared between the music therapy and non-music therapy groups.
Secondary objectives and endpoints	
Secondary objectives are to evaluate the effect of music therapy by comparing the two groups (with and without music therapy) on:
 
 a. Changes in anxiety levels between the first and the third chemotherapy sessions, measured using the STAI State score (before the first session and before the third session). b. Changes in anxiety levels between the first and the last chemotherapy sessions, measured using the STAI State score (before the first session and before the last session). c. Changes in quality of life, measured using the PROMIS-29 questionnaire at study inclusion, at the end of the third chemotherapy session, and at the end of all chemotherapy sessions. d. The presence of anticipatory nausea (i.e., nausea occurring before chemotherapy administration) assessed before the first three chemotherapy sessions and before the last chemotherapy session, using a 0–10 numeric rating scale.
Inclusion criteria	
 1. Female patient with localized breast cancer 2. Indication for adjuvant or neoadjuvant chemotherapy 3. Age ≥ 18 years 4. Signed informed consent 5. Patient covered by a national health insurance system
Exclusion criteria	
 1. Metastatic breast cancer 2. Triple-negative breast cancer (HR–: ER–, PR– and HER2–) 3. Patient not eligible for curative surgery 4. Prior treatment with chemotherapy 5. Uncorrected hearing loss 6. Pregnant or potentially pregnant woman, or breastfeeding 7. Presence of a major depressive episode or psychotic disorder at the time of the diagnostic consultation 8. Patient unable to understand French 9. Cognitive impairment or inability to understand study requirements 10. Vulnerable patient under legal protection (safeguard of justice, guardianship, or curatorship)

E) DESCRIPTION OF STUDY INTERVENTIONS

Description of the Music Therapy Intervention

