In the experimental group, a music therapy session conducted by a certified music therapist will be offered to the patients. The session will take place before the administration of chemotherapy during the 1st, 2nd, and 3rd treatment cycles. Each session will last 1 hour.

The activity program will be defined during the first individual session. The sessions will follow three progressive processes:

Activities	Patient Involvement
Instrumental music (violin, guitar, singing) Relaxation suggestions (e.g., imagery associated with the music resonating in the body) Suggestion of music listening at home Invitation to instrumental improvisation Vocal warm-up	Active listening Attention to bodily sensations
Instrumental music as an introduction Invitation to instrumental improvisation	Selection of music pieces

Vocal warm-up Suggestion to use music as a relaxation tool at home	Physical involvement in playing a musical instrument (hang, senzula, percussion instruments)
Musical introduction based on the patient's choice Vocal warm-up Singing an existing song or engaging in songwriting (brainstorming, selecting a melody, singing the composition with the music therapist) Discussion on the use of music to improve mood and reduce feelings of fatigue	Active listening or instrumental play Songwriting Verbalization of emotional experiences

Description of Quality-of-Life Questionnaires:

Participants will be asked to complete the following quality of life questionnaires (see the assessment schedule for the timing of questionnaire administration):

STAI (State/Trait):

The State Trait Anxiety Inventory (STAI), developed by Spielberger et al. (1983), is a self assessment questionnaire. The French version was validated by Bruchon Schweitzer et al. in 1993 (Manuel de l'inventaire d'anxiété état trait – forme Y).

This scale includes two components:

- State Anxiety, which reflects the patient's current emotional state and allows assessment of nervousness and worry during the session.
- Trait Anxiety, which reflects the patient's general and habitual emotional state.

PROMIS 29:

The PROMIS 29 Profile v2.0 assesses pain intensity using a single numeric rating item (0 to 10) and evaluates seven health domains (physical function, fatigue, pain interference, depressive symptoms, anxiety, ability to participate in social roles and activities, and sleep disturbance), using four items per domain.

STUDY ASSESSMENT SCHEDULE

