VISITS	INCLUSION PERIOD	TREATMENT PERIOD						FOLLOW UP PERIOD	
Dates des visites		Cycle 1		Cycle 2		Cycle 3		Last cycle	M6 end of treatment
Delay		Before start of musicotherapy	End of chemotherapy	Before start of musicotherapy	End of chemotherapy	Before start of musicotherapy	End of chemotherapy		
Inclusion / Exclusion criteria	X								
Informed consent	X								
Randomisation (2:1)	X								
PRO (Patient Reported Outcome)									
STAI YB (trait)		X							X
STAI YA (état)		X	X	X	X	X	X		
QLQ C30		X					X	X	
BR23		X					X	X	
Numerical scale 0-10 (nausea)		X					X	X	
INTERVENTION									
Arm 1 : musicotherapy		Before chemotherapy		Before chemotherapy		Before chemotherapy			
Arm 2 : control

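### Anticipatory nausea is defined by four pre-chemotherapy ratings, but the assessment schedule provides three, of which only the Cycle 1 rating is certain to be pre-chemotherapy

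*Protocol*

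**What the plan says.** Protocol, section D, secondary objectives and endpoints, item d, defines anticipatory nausea as "nausea occurring before chemotherapy administration" and says it is to be "assessed before the first three chemotherapy sessions and before the last chemotherapy session, using a 0–10 numeric rating scale". That is four time points, each before a session.

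Protocol, Study Assessment Schedule, splits each of Cycles 1 to 3 into two columns: "Before start of musicotherapy" and the end of chemotherapy. The last cycle has a single column, and its timing cell in the Delay row is blank. The row "Numerical scale 0-10 (nausea") has three crosses: Cycle 1 in the before column, Cycle 3 in the end-of-chemotherapy column, and the last cycle. Both Cycle 2 columns and the Cycle 3 before column are empty in that row.

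No other part of the protocol schedules a nausea rating.

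**The concern.** Item d and the schedule are both current text and cannot both be carried out as written. By the protocol's own definition, a rating taken once chemotherapy has been given is not anticipatory nausea, so the Cycle 3 cross does not stand in for the missing pre-Cycle 3 rating.

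What is at stake is the between-group comparison on this endpoint. Patients with prior chemotherapy are excluded (exclusion criterion 4), and the Cycle 1 before rating is taken ahead of the first music session. That rating can describe the groups at the start but cannot show an effect of the intervention. The comparison depends on the later ratings, and the schedule secures none of them. An analysis plan cannot recover a rating that was never collected, nor turn one taken after chemotherapy into one taken before it.

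**Working it through.** The protocol states no power or precision figure for this endpoint, so there is nothing to reproduce. The check is a comparison of two passages and a count.

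**Inputs**
- Ratings required per patient: 4 (item d).
- Crosses in the nausea row: 3 (Study Assessment Schedule).
- Patients: 27 (section A, "Number of subjects").
- Allocation: 2:1 (section D, design), used only for the split by arm.

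**Step 1: is the table read correctly?** The nausea row has its full set of ten cells. The STAI State row in the same table fills all six columns of Cycles 1 to 3, so the columns line up. However the crosses are aligned, three cannot supply four ratings.

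**Step 2: item d against the schedule**

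| Required by item d | Schedule | Result |
|---|---|---|
| Before session 1 | Cycle 1, before music therapy | Matches |
| Before session 2 | No cross in Cycle 2 | Absent |
| Before session 3 | Cycle 3, end of chemotherapy only | Wrong time |
| Before last session | Last cycle, timing blank | Undetermined |

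**Step 3: count, if the schedule is followed and all 27 patients complete every planned rating**
- Planned: 27 × 4 = 108.
- Valid if the last-cycle rating is taken after chemotherapy: 27 × 1 = 27, and 27/108 = 25%.
- Valid if the last-cycle rating is taken before chemotherapy: 27 × 2 = 54, and 54/108 = 50%.
- Absent or mistimed: 108 − 54 = 54 (50%) to 108 − 27 = 81 (75%).

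**Step 4: post-baseline ratings only**
- Planned: 27 × 3 = 81.
- Certainly absent or mistimed (Cycles 2 and 3): 27 × 2 = 54.
- Undetermined (last cycle): 27 × 1 = 27.
- Assured: 0.

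With 2:1 allocation the arms are 27 × 2/3 = 18 and 27 × 1/3 = 9. At best, then, the comparison rests on one post-baseline rating from each of 18 and 9 patients; at worst, on none.

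The percentages in step 3 are 1/4 and 2/4 per patient and do not depend on the number of patients.

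**The case against.** The strongest reply is that item d is explicit about both definition and timing, so a site working from it would collect all four ratings. The documents do not say which text prevails. The section on questionnaires does refer the reader onward ("see the assessment schedule for the timing of questionnaire administration"), but that sentence introduces the quality-of-life questionnaires, and only STAI and PROMIS-29 are then described. It does not establish that the schedule governs the nausea scale. This stands: the counted loss is conditional on staff following the schedule. It does not remove the contradiction.

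Second, the last-cycle cross is ambiguous rather than wrong. Item d places that rating before the session, and staff could read the cross that way. This also stands, and it is why the loss is a range. A reader might infer that most of the planned data are lost, but only two of the four ratings, exactly half, are certainly absent or mistimed. On the other side, the column sits under the follow-up period and is shared with the quality-of-life forms, which item c places at the end of all sessions. The favourable reading therefore cannot be assumed.

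Third, two inferences go beyond the text. The nausea crosses coincide with those of the QLQ C30 and BR23 rows, so one might conclude that the row was copied from them; the documents show identical marks, not their cause. One might also expect the Cycle 3 value to be reported as anticipatory nausea, but the row is labelled only as nausea and no analysis plan is at hand. Neither inference is needed for the point.

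**Conclusion.** The inconsistency is real. Item d requires four pre-chemotherapy ratings; the schedule matches one, omits one, places one at the end of chemotherapy, and leaves one without a stated time. If the schedule is followed, 54 to 81 of 108 planned ratings (50% to 75%) are absent or do not measure the endpoint, and no post-baseline rating is assured. The counts assume 27 patients with complete follow-up; the lower end of the range also assumes that the last-cycle rating is taken before chemotherapy.

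This should be fixed, but its reach is limited. A reader might infer that the trial's main comparison is compromised. The documents do not support that: the primary endpoint uses STAI State before and after the first three sessions, and all six of those time points are marked in the schedule. The point concerns one secondary endpoint whose intent, as stated in item d, is clear.

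**What to change.** Reconcile the schedule with item d:

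- Place the nausea scale in the before columns of Cycles 1, 2 and 3.
- Give the last cycle an explicit pre-chemotherapy time point and place the scale there.
- Delete the cross at the end of Cycle 3 chemotherapy, or keep it under a label showing that it is a separate measure and not anticipatory nausea.

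The cost is small: a correction to the schedule and the case report form for a single 0–10 item. At Cycles 1 to 3 the patient already completes STAI State in the before column, so no new contact is needed. Item b also calls for a STAI State score before the last session, so a pre-chemotherapy time point there would serve both.

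If ratings have already been collected, report the time at which each was actually taken, and do not present values from the end of chemotherapy as anticipatory nausea.

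### The last scheduled visit, M6, does not fit the stated 5-month participation on either reading, fits the 24-month study on only one, and serves no defined endpoint

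*Protocol*

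**What the plan says.** Protocol section A (Clinical trial identification) states "Inclusion period 18 months", "Subject participation duration 5 months" and "Overall duration 24 months".

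The Study assessment schedule has two follow-up columns: the last cycle and, after it, "M6 end of treatment". No text says from which date the six months run. By column position, the only mark in the M6 column is on the STAI YB (Trait) row, whose other mark is before the first music therapy session. The STAI YA (State) row is marked before and after each of cycles 1 to 3 and nowhere later.

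In section D, the primary endpoint opens by naming both forms: "Anxiety will be assessed using the STAI scale (Trait form YB and State form YA". The comparison it then defines is on State scores only: "The mean pre- and post-chemotherapy difference in STAI State scores will be compared between the music therapy and non-music therapy groups". Secondary endpoints a and b use the State score, c uses PROMIS-29 and d uses a nausea scale. None has a time point later than the end of all chemotherapy.

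**The concern.** The participation duration tells patients, ethics reviewers and site staff how long each patient is in the study. A visit scheduled beyond it means that either the duration or the schedule is misstated. Because M6 has no origin, staff cannot tell when to hold it, and the two possible dates differ by the whole chemotherapy period. On the later date, patients recruited near the end of inclusion could not reach the visit before the study closes at month 24, so the final Trait score would be missing according to entry date.

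There is also a question of purpose. The visit holds a single questionnaire, and no listed endpoint takes a value from it. Meanwhile secondary endpoint b depends on a State score before the last session, for which the schedule has no mark.

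**Working it through.** **Inputs.** From section A: inclusion 18 months, participation 5 months, overall 24 months, 27 patients. From the Study assessment schedule: last visit at M6, origin undefined. Chemotherapy length, c months, is not given anywhere in the protocol. It is left as a symbol, then shown for an assumed 3 to 5 months.

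**Formula.** Last visit of the last entrant = inclusion period + time from entry to last visit.

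**The plan's own figures.** 18 + 5 = 23 months, which fits within 24 with one month to spare. Without M6, the three durations in section A agree with each other.

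**Reading A: M6 is month 6 from inclusion.**
- Participation: 6 months, against 5 stated.
- Last visit of the last entrant: 18 + 6 = 24 months, exactly the stated overall duration.

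**Reading B: M6 is six months after the end of treatment.**
- Participation: c + 6 months, against 5 stated.
- Last visit of the last entrant: 18 + c + 6 = 24 + c months, beyond 24 for any c above zero.
- Latest entry that completes M6 by month 24: 24 − 6 − c = month 18 − c.

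| Assumed c (months) | Participation (months) | Last visit (month) | Latest entry completing M6 by month 24 |
|---|---|---|---|
| 3 | 9 | 27 | month 15 |
| 4 | 10 | 28 | month 14 |
| 5 | 11 | 29 | month 13 |

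With uniform accrual (a further assumption), 27 / 18 = 1.5 patients enter per month. Those entering in the last c months of inclusion number 3 × 1.5 = 4.5 to 5 × 1.5 = 7.5, or 17% to 28% of 27.

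**Endpoints against the schedule.**

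| Endpoint (section D) | Measure | Last time point | Uses M6? |
|---|---|---|---|
| Primary | STAI State | Third session | No |
| Secondary a | STAI State | Before third session | No |
| Secondary b | STAI State | Before last session | No; no mark on the STAI YA row at the last cycle |
| Secondary c | PROMIS-29 | End of all chemotherapy | No |
| Secondary d | Nausea scale | Before last session | No |

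None of the five endpoints uses an M6 value or defines a Trait comparison.

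**The case against.** The strongest reply is that the label can be read as an end-of-treatment visit held at about month 6 from inclusion. The match of 18 + 6 with the stated 24 months supports that. The discrepancy is then one month of participation, with no overrun and no late entrant losing a visit. This stands as far as it goes: nothing in the protocol favours the post-treatment reading. A reader might infer that both durations are wrong whatever M6 means, or that late entrants will lose the visit. The documents do not support either; both follow only if M6 runs from the end of treatment. The 5-month figure, however, fails even on the milder reading.

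Second, a reader might infer that the Trait score answers no declared question. That goes too far. The primary endpoint names the Trait form as an instrument, the primary objective concerns anxiety levels in general, and a statistical analysis plan that is not at hand may say how Trait is analysed. What remains is narrower: among the objectives and endpoints that the protocol itself lists, none defines a Trait comparison or takes a value at M6.

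Third, the primary endpoint data end at cycle 3, and all secondary endpoints end by the close of chemotherapy. That is correct, and it limits the weight of the point.

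**Conclusion.** The contradiction between the M6 visit and the 5-month participation is established. It needs no assumption beyond reading M6 as a count of six months, and it affects all 27 patients. Its size is one month if M6 counts from inclusion, and one month plus the chemotherapy period if it counts from the end of treatment.

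The conflict with the 24-month duration is conditional on the post-treatment reading. The overrun then equals the chemotherapy length, whatever that is. Study end at month 27 to 29 also needs the assumed 3 to 5 months of chemotherapy, and the 17% to 28% of patients without M6 by month 24 needs uniform accrual as well. These figures show what is at stake under one reading; they are not a forecast.

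The M6 Trait score is a declared instrument without a declared comparison. The primary analysis is unaffected. The point should be put right because it concerns a stated protocol figure and the feasibility of the last visit, and because the correction is small.

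**What to change.** Reconcile section A, section D and the Study assessment schedule in one of two ways.

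1. **Keep the visit.** State whether M6 counts from inclusion or from the end of treatment. Correct the participation duration and, if M6 counts from the end of treatment, the overall duration too. State the endpoint that the M6 Trait score serves. The cost is an amendment of a few lines, plus a longer study under the post-treatment origin.
2. **Remove the visit.** This also needs an amendment, and it gives up the only measurement after the last cycle. It does not by itself make the 5 months correct: because chemotherapy length is not stated, the sponsor must check that 5 months covers inclusion to the last cycle. If it does, 18 + 5 = 23 fits within 24.

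In either case, add the STAI State before the last cycle to the schedule, since secondary endpoint b cannot be computed without it. That costs one more questionnaire at a visit already planned.

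### Baseline quality of life and STAI Trait are scheduled at Cycle 1, after open-label randomisation, although endpoint c sets the quality-of-life baseline at inclusion

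*Protocol*

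**What the plan says.** The design list in section D of the Protocol describes the trial as "Open-label study" and "Randomized study (2:1 allocation ratio", with 27 subjects.

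In the Study Assessment Schedule, eligibility, consent and randomisation ("Randomisation (2:1") are marked in the inclusion column. Every questionnaire row (STAI YB, STAI YA, QLQ C30, BR23, nausea scale) is empty in that column. Each has its first mark in the Cycle 1 column headed "Before start of musicotherapy".

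The endpoint text in section D sets these times:

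- Secondary endpoint c: "Changes in quality of life, measured using the PROMIS-29 questionnaire at study inclusion", with later assessments after the third session and after all sessions.
- Secondary endpoint a, on State anxiety: "before the first session and before the third session". Endpoint b also starts before the first session.
- Primary endpoint: "The STAI State score will be collected before and after chemotherapy administration during the first three chemotherapy sessions".

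Section E refers the reader to the schedule for the timing of questionnaires, so no other text supplies an assessment at inclusion.

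**The concern.** Endpoint c and the schedule give different times for the same baseline, and the difference matters because randomisation lies between them. A quality-of-life form completed at inclusion can precede allocation. One completed at Cycle 1 cannot.

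In an open-label trial, a patient who has learned that she will, or will not, receive music therapy may answer a self-report form differently. If so, the baseline of endpoint c is no longer independent of the arm. Part of any treatment comparison would then be a reaction to allocation that occurred before the first session.

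The same applies to the Trait form. No endpoint compares Trait scores, so I assume that its main use would be as a baseline descriptor or covariate. A covariate measured after allocation is less safe in that role than one measured before. No later analysis can recover a pre-randomisation score that was never collected.

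**Working it through.** **Step 1: schedule against endpoint text.**

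| Measure | Baseline time in endpoint text | First mark in schedule | Agreement |
|---|---|---|---|
| Quality of life (endpoint c) | Study inclusion | Cycle 1, pre-session | No |
| STAI Trait | No time given | Cycle 1, pre-session | No conflict, but after randomisation |
| STAI State (primary, a, b) | Before the first session | Cycle 1, pre-session | Yes |

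The instruments also differ. Endpoint c and section E name PROMIS-29. The schedule has no PROMIS-29 row and lists QLQ C30 and BR23. Whichever is intended, no quality-of-life form is scheduled at inclusion.

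**Step 2: do patients know their arm at Cycle 1?** The protocol does not say when allocation is disclosed. Knowledge is inferred from the open-label design, randomisation at inclusion, and the absence of anything that delays disclosure. It is probable, not stated.

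**Step 3: effect on endpoint c.** Let q be the between-arm difference (music minus control) that knowledge of the arm adds to the baseline score.

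- Change = later score − baseline. If the later scores do not carry the shift, the between-arm difference in change moves by −q.
- If the later scores carry the same shift, it moves by q − q = 0.

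The size therefore lies between 0 and q.

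**Step 4: effect on the State endpoints.** Let k be the corresponding shift in a pre-session State score. Assume that post-session scores do not carry it and that the primary averages the three session differences (post − pre).

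| Where the shift occurs | Primary | Endpoint a (pre-Cycle 3 − pre-Cycle 1) |
|---|---|---|
| Pre-Cycle 1 only | (−k + 0 + 0)/3 = −k/3 | 0 − k = −k |
| All three pre-scores | (−k − k − k)/3 = −k | k − k = 0 |

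For k of one point, the primary moves by between 1/3 and 1 point, and endpoint a by 1 point or by none. Endpoint b behaves like a: k if the shift is confined to Cycle 1, 0 if it lasts to the final session.

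On direction, if expecting music lowers the pre-score in the music arm, or disappointment raises it in the control arm, then k is negative. The music arm's fall then looks smaller relative to control.

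**Step 5: what is not known.** The protocol gives no value for q or k and no standard deviation, so neither shift can be set against an expected effect. With 2:1 allocation of 27, the arms are 27 × 2/3 = 18 and 27 × 1/3 = 9.

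**The case against.** The strongest reply concerns State anxiety. The primary and endpoints a and b are defined from scores taken on the day of the session, and section E describes State as the patient's current condition. The Cycle 1 timing is therefore correct for State. A form completed at inclusion measures a different moment and cannot replace it. Pre-scores at Cycles 2 and 3 follow randomisation under any schedule, and the post-scores are unblinded self-reports too. All of this stands. A reader might infer that the schedule contradicts the State endpoints, or that it biases a and b by a full k. The first is not so, and the second is only one of the two scenarios in the working. Nor would moving forms cure reporting bias that comes from the open-label design.

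Three further replies have some force:

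- Trait is meant to reflect a habitual disposition and is the measure least likely to move on allocation. That makes the Trait part the weaker one, but does not argue for measuring it late.
- Section E defers to the schedule for timing, which could be taken to give the schedule precedence. This softens the conflict without removing it, because endpoint c still states a different time and the schedule keeps the inclusion and treatment periods apart.
- A patient who withdraws on learning her arm would also lack every session score, so a baseline for her adds little to the primary analysis.

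**Conclusion.** The point holds for quality of life and Trait. The quality-of-life baseline time in endpoint c conflicts with the schedule, and both forms are first collected after randomisation in an open-label trial. The possible distortion of endpoint c is between 0 and q points, with q unknown. This rests on patients knowing their arm by Cycle 1, which is likely but not stated.

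For State anxiety there is no inconsistency. Reporting bias in the pre-session scores is possible, with the range shown above, and the change proposed here does not remove it. This is a weakness worth correcting by amendment. It does not by itself invalidate the trial.

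**What to change.** 1. In the Study Assessment Schedule, place STAI YB and the baseline quality-of-life form or forms in the inclusion column. State that they are completed after consent and before randomisation.
2. Reconcile the instrument: PROMIS-29 in endpoint c and section E, QLQ C30 and BR23 in the schedule.
3. Optionally, add one STAI State form at the same point as a pre-randomisation covariate. Keep the pre-session State scores on the day, as the primary and endpoints a and b require.
4. State when the patient is told her allocation.

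The cost is a schedule amendment. Two forms move if quality of life is PROMIS-29 (STAI YB and PROMIS-29), three if it is QLQ C30 and BR23; the optional State form adds one. The inclusion visit already exists. The drawback is that these baselines are taken somewhat earlier than Cycle 1, by an interval that the protocol does not state.
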